^j Subject Education and training on Diabetes management and use of off-loading device will be done as and when required

^k The AE reporting will begin from the application of the first dose of the IP from the Baseline Visit

^l Debridement of ulcer as and when necessary during site visit

^m Nutritional information should be provided to Subject as and when necessary

ⁿ Photographs of both the legs will be taken from various angles to ensure that there are no more than three ulcers on both the legs

^o In case the ulcer/wound closes within 12-weeks of Treatment Phase, the Subject will immediately enter the 12-weeks of Follow-Up Phase. In case of the Subject, whose Target Ulcer reopens during 12-weeks of Treatment Phase (within 84 days from Baseline) which is prior to the confirmation of Target Ulcer closure, the Subject would be given the treatment to complete 12-week of Treatment Phase

^p During Follow-Up Phase, if the Target Ulcer has reopened after confirmation of its closure, the Subject will still be continued with the Follow-up assessment.

^q This window period is from the Screening Visit

^r EOT is at week 12 visit or any visit on which first observation of Target Ulcer closure has happened or treatment is Stopped

^s EOS is at week 24 visit or any visit on which the Subject exits the Study

^t Window period of ±3 days will be allowed for each Treatment visit as well as FU1 and FU2 visits and window period of ±5 will be allowed for FU3 and FU4

Note: *Dispensing of Wound dressing material will be provided as long as required

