4.4 END OF STUDY DEFINITION

A participant is considered to have completed the Study if he or she has completed all phases of the study including the last visit or the last scheduled procedure shown in the Schedule of Activities (SoA), [Section 1.3](#). The end of the study is defined as completion of the last visit or procedure shown in the SoA in the trial. In addition, if Subject is discontinued or withdrawn from the Study, the last recorded visit of such Subject shall be considered as the End of Study.

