7.2 PARTICIPANT DISCONTINUATION/WITHDRAWAL FROM THE STUDY

Participants are free to withdraw from participation in the Study at any time. If the withdrawal happens during the Treatment /Follow up Phase, the last visit prior to withdrawal will be treated as EOT/EOS visit and corresponding CRF will be completed by the Investigator.

Subjects who sign the informed consent form (ICF) and are randomized but do not receive the study intervention will not be replaced and will not be part of ITT Population.

Subjects who sign the ICF, and are randomized and receive the study intervention, and subsequently withdraw, or are withdrawn or discontinued from the study, will not be replaced and yet be part of ITT Population.

Subjects must be discontinued from the Study after randomization if any of the following events occur (Stopping or Discontinuation Rules for Individual Subjects):

1. A Subject withdraws consent
2. Investigator recommends that the Subject should discontinue the participation in the Study
3. Subject misses two consecutive Weekly Visits during Treatment Phase
4. If the Target Ulcer and the adjoining wound merge together and if the Investigator opines that following the Target Ulcer is difficult. A detailed note by the Investigator will be recorded in the e-CRF outlining reasons for such merger in line with the preceding measurement of Target Ulcer
5. If Subject requires hospitalization for more than two consecutive weeks during the Study
6. The Subjects with treatment compliance of less than 80% or more than 120% during the week, will be considered treatment non-compliant for that week. If such non-compliance is observed for more than three weeks, and if the blinded Investigator opines that it may affect the outcome of the Study, then the Subject shall be considered non-compliant for the Study and shall be discontinued from the Study
7. If the blinding of a Subject is compromised
8. Any form of major protocol violation
9. The Target Ulcer increases in size (more than 30%) for two consecutive weeks or requires deep, surgical debridement for more than two occasions during the Treatment Phase to address Target Ulcer deterioration
10. The Target Ulcer becomes infected requiring topical antimicrobial treatment
11. If Subject develops osteomyelitis or cellulitis during the Study on the foot having the Target Ulcer
12. If female Subject becomes pregnant, during the study
13. If Subject misses 6 consecutive dressings

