- Assessment of local pain in terms of 11-point (0-10) universal pain scale for the Target Ulcer (See *Attachment 4*)
- Assessment of local edema in terms of 5-point (0-4) edema scale for the Target Ulcer (See *Attachment 4*)
- Assessment of local erythema in terms of 5-point (0-4) erythema scale for the Target Ulcer (See *Attachment 4*)
- Clinical assessment of infection status of non-Study ulcer(s)
- Subject education on diabetes management and off-loading as and when required
- Recording of concomitant medications
- AE recording
- Nutritional information (i.e., the importance of diet in controlling glucose levels) will be provided to and reviewed. Further counseling to the Subject will be available on request during the course of Study
- Study Diary review will be done by unblinded Investigator for treatment compliance check and use of offloading device at each visit of the Study Nurse to the investigator Site

Follow-up Visit Week 14 to Week 24 (FU1 to FU4) [V15/Day 98 to V18/Day 168 (Window period $\pm 3/\pm 5$ days)]

The Subjects whose Target Ulcer is closed (first observation of Target Ulcer Closure) or the Subject who completes the 12-weeks of Treatment Phase, whichever is earlier, will immediately enter the Follow-Up (FU) Phase of 12-weeks. All Subjects who enter the Follow-Up Phase are required to attend the Follow-up visit FU1-two weeks after EOT; FU2-four weeks after EOT, FU3-eight weeks after EOT and FU4-twelve weeks after EOT, regardless of whether the Target Ulcer is open/closed/re-opened.

For the Subjects whose Target Ulcer has closed within the 12-week Treatment Phase, the 12-week Follow-Up Phase is divided into 4-week Closure Confirmation period and 8-week Observation period. The Closure Confirmation period will be of total four weeks with two visits two weeks apart for confirming initial closure of the Target Ulcer. The Observation period will be of total eight weeks with two visits, four weeks apart for assessing quality of healing, progress of ulcer closure and AEs, if observed.

For the Subjects whose Target Ulcer has not closed within 12-week Treatment Phase, the 12-week Follow-Up Phase will be considered as 12-week Observation period.

Subjects who have entered the Follow-Up Phase will be subjected to SoC treatment as deemed necessary by the Investigator. Unless recommended by the Investigator otherwise, SoC during the Follow-Up Phase will be self-administered by the Subject.

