9.3 POPULATIONS FOR ANALYSES

For this Study, analysis will be done on ITT Population (Safety Evaluable Population), FAS Population (Efficacy Evaluable Population) and PP Population.

The ITT Population i.e. Safety Evaluable Population will include all those Subjects who are randomized and received at least one dose of the study treatment.

The FAS Population (Efficacy Evaluable Population) will include all randomized Subjects who has had at least six weekly assessments for Target Ulcer Closure or has Target Ulcer closed earlier than six weeks.

The PP Population will include all randomized Subjects who have completed the Study without any major protocol deviation.

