9.4.2 ANALYSIS OF THE PRIMARY EFFICACY ENDPOINT

The primary efficacy analysis will be performed on all Subjects in FAS Population (Efficacy Evaluable Population) and PP Population comparing Group 1 (Galnobax® plus SoC) and Group 2 (SoC only) only.

Proportion of Subjects achieving Target Ulcer closure within 12 week Treatment Phase (EOT) = [Number of Subjects having Target Ulcer closed by treatment at or before week 12 (84 ± 3 days)]/[Total Number of Subjects in the Population].

The logistic regression analysis will be used for the primary efficacy analysis for the proportion of Subjects achieving Target Ulcer closure within 12-week Treatment Phase, considering Target Ulcer closed (Yes/No) as dependent variable and treatment group, ulcer type (plantar or non-plantar), and site as independent factors and baseline ulcer size as continuous covariate.

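### The PP Population depends on completing follow-up after the primary endpoint is settled, so its closure rates can be biased in either direction

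*Combined protocol and SAP*

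**What the plan says.** Section 9.3 defines the population: "The PP Population will include all randomized Subjects who have completed the Study without any major protocol deviation". The Definitions table near the front of the protocol gives the same rule.

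Section 4.4 says what completion means: "A participant is considered to have completed the Study if he or she has completed all phases of the study including the last visit". It also labels a discontinued subject's last recorded visit as that subject's End of Study, and the Schedule of Activities does the same: "EOS is at week 24 visit or any visit on which the Subject exits the Study". That label dates the exit; it does not turn the subject into a completer. The last visit is defined in Section 8 as "FU4-twelve weeks after EOT".

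Section 7.2 lists events after which a subject must leave the Study, not only the treatment. Three of them describe Target Ulcer worsening:
- Item 9: "The Target Ulcer increases in size (more than 30%) for two consecutive weeks", or deep surgical debridement on more than two occasions in the Treatment Phase.
- Item 10: Target Ulcer infection that requires topical antimicrobial treatment.
- Item 11: osteomyelitis or cellulitis on the foot with the Target Ulcer.

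None of these events is among the examples of major deviations in Section 10.1.8.

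Section 9.4.2 uses PP for the primary endpoint: "The primary efficacy analysis will be performed on all Subjects in FAS Population (Efficacy Evaluable Population) and PP Population". It sets no order between the two populations, and the denominator of the proportion is the population being analysed.

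**The concern.** A per-protocol set is normally read as confirming the main result in subjects who adhered. Here membership also depends on staying to the end of follow-up, and that depends partly on the outcome. A subject who adhered to treatment and was removed because the ulcer deteriorated is a non-closer. By the Section 9.4.2 formula, that subject counts as not closed in the FAS once six weekly assessments are in hand, yet is absent from PP. A subject with a confirmed closure who leaves before FU4 is a success, and is absent too.

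The PP comparison therefore conditions on outcome-related events and on events after the endpoint is known. At stake is a second primary-endpoint result that could appear to strengthen, weaken or contradict the FAS result for reasons unrelated to adherence.

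**Working it through.** **1. The plan's own figure.** Section 9.2 gives 39% vs 60%, two-sided alpha 0.05 and 90% power. The pooled formula is n = [1.96·√(2·0.495·0.505) + 1.2816·√(0.39·0.61 + 0.60·0.40)]² / 0.21² = (1.386 + 0.886)² / 0.0441. This is just over 117, so 118 per arm. The plan's 120 per arm gives 90.7% power, and 240/0.80 = 300 randomized, or 150 per arm. The sample size reproduces, and its closure rates are used below.

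**2. Timing.** (EOT is end of treatment.)
- Closers: the endpoint is settled at FU2 (EOT + 4 weeks) and PP membership at FU4 (EOT + 12 weeks), a gap of 8 weeks.
- Non-closers who stay on schedule: the endpoint is settled at week 12 and membership at week 24, a gap of 12 weeks.
- Example: a subject closing at week 5 is confirmed near week 9 and completes near week 17, so week 24 is the maximum, not the rule for all.

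**3. Formula.** Let p be the closure rate in all randomized subjects of an arm, e the share of the arm lost as non-closers, and c the share lost as confirmed closers. Then PP rate = (p − c)/(1 − e − c). With c = 0 this is p/(1 − e).

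**4. Results.** The documents give no exit shares by reason or arm, so all values of e and c are assumptions, as is the 45% rate. Differences are taken before rounding.

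| True closure, Galnobax vs SoC | Non-closer exits e | PP rates | PP difference | True difference |
|---|---|---|---|---|
| 60% vs 39% | 10% vs 10% | 66.7% vs 43.3% | 23.3 points | 21 points |
| 60% vs 39% | 15% vs 5% | 70.6% vs 41.1% | 29.5 points | 21 points |
| 60% vs 39% | 5% vs 15% | 63.2% vs 45.9% | 17.3 points | 21 points |
| 45% vs 45% | 15% vs 10% | 52.9% vs 50.0% | 2.9 points | 0 |
| 39% vs 39% | 15% vs 5% | 45.9% vs 41.1% | 4.8 points | 0 |

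Loss of closers works the other way. For SoC at 39% with e = 10% and c = 7%, the PP rate is 0.32/0.83 = 38.6%, below the true rate despite the lost non-closers.

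**5. Effect on a test.** Take 39% closure in both arms, 150 randomized per arm and a pooled two-proportion z test. The chance of a significant result favouring the arm with more removals should be 2.5%. It is 5.8% with exits of 10% vs 5%, and 12.3% with 15% vs 5%. A simulation of 200,000 trials gave 5.9% and 12.4%. With removed subjects kept as not closed it stays near 2.5%. The plan uses logistic regression with covariates, so these figures are indicative.

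**6. What the FAS already carries.** A worsening exit before six assessments is missing from the FAS too. Suppose half of the exits are that early.
- At 60% vs 39% with 10% exits per arm, the FAS gives 0.60/0.95 = 63.2% vs 0.39/0.95 = 41.1%, or 22.1 points. PP at 23.3 adds 1.2.
- At 45% in both arms with 15% vs 10%, the FAS gives 0.45/0.925 vs 0.45/0.95, or 1.3 points. That is part of PP's 2.9.

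If all exits come after six assessments, the FAS shows the true rates and the whole shift belongs to PP.

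**The case against.** The strongest defence is that PP decides nothing. Section 4.2 says that the efficacy analysis uses the FAS, Section 9.2 powers the trial on it, and no decision rule refers to PP. This stands and limits the weight of the point. It does not remove it, because Sections 9.4.1 and 9.4.2 still list PP beside the FAS without rank.

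A separate SAP is promised before database lock, and Section 9.4.7 leaves missing data to it. That SAP could help, but the membership rule is already fixed in Section 9.3. Methods for missing data work inside a population and do not return subjects to it.

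The removal rules are also narrower than they may look, and this stands:
- Infection alone does not remove a subject. Section 6.5 allows oral or parenteral antibiotics, and item 10 applies only where topical treatment is required.
- If a topical agent is actually used on the Target Ulcer, Sections 10.2.1 and 10.1.8 make that a major deviation, so some item 10 subjects would leave PP in any case.
- Two consecutive weeks of growth can hardly be seen at follow-up visits two to four weeks apart.
- Missing FU3 alone is not clearly failure to complete.

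A reader might infer that the arm with more deterioration will look better, or that the rule favours Galnobax. The documents do not support either. They give no removal rates by arm. An arm overtakes the other only when true rates are close or exits differ enough: for example, 36% with 15% removed (42.4%) against 39% with 5% removed (41.1%). If SoC deteriorates more, the bias runs against Galnobax. Nor are both rates necessarily inflated, since lost closers pull a rate down.

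**Conclusion.** The point holds as a flaw in the PP definition, with a bias whose direction cannot be known in advance. The textual part needs no assumption: PP membership runs 8 to 12 weeks past endpoint determination, and mandatory removals for worsening empty the PP denominator of known non-closers.

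The size is conditional. With assumed non-closer exits of 5% to 15% per arm and no lost closers, a true 21-point difference could appear as anything from 17.3 to 29.5 points. The 20% drop-out allowance in Section 9.2 is a margin for reaching the FAS target, not a worsening rate, so it does not fix the exit shares.

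The text should be corrected before database lock. It does not by itself undermine the powered FAS analysis, although early worsening exits affect the FAS through its own six-assessment rule.

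**What to change.** 1. In Section 9.3 and the Definitions table, define PP as randomized, treated subjects with no major protocol deviation up to determination of the primary endpoint (FU2 for closers, end of the Treatment Phase for others), whether or not they complete later follow-up.
2. Keep in PP, as not closed, subjects discontinued under Section 7.2 items 9 to 11 before a confirmed closure, including those with fewer than six assessments. Keep confirmed closers as closed whatever happens later. State that the topical treatment which triggers an item 10 discontinuation does not by itself count as a major deviation for PP membership.
3. In Sections 9.4.1 and 9.4.2, state that the FAS analysis is decisive and the PP analysis supportive, in line with Sections 4.2 and 9.2.
4. Reconcile item 9 (removal for repeated deep debridement) with Section 9.4.9 (treatment failure after more than two surgical debridements) on how such subjects count in each population.

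This costs protocol and SAP wording only. No removal rule, clinical management or data collection changes. The small downside is that PP will differ less from the FAS and may give a less favourable figure.

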9.4 STATISTICAL ANALYSES

9.4.1 GENERAL APPROACH

Before database lock, a statistical analysis plan (SAP) will be issued as a separate document, providing the detailed methods for analyses outlined below. Any deviation from the planned analyses will be described and justified in the final integrated clinical Study report.

A maximum of 350 Subjects will be competitively recruited at 40 sites from the DFU Subject population as described in [section 4.1](#).

The number and percentage of all the DFU Subjects entering and completing the clinical Study will be provided across treatment groups. The summarization of primary reason of discontinuation will also be provided across treatment groups.

For this Study, analysis will be done on ITT Population (Safety Evaluable Population), FAS Population (Efficacy Evaluable Population) and PP Population.

The continuous data will be summarized by treatment Group using descriptive statistics (number of Subjects [n], Mean, Standard Deviation [SD], Median, Minimum and Maximum [Range]). Categorical data will be summarized by treatment group using frequency count (n) and percentages (%).

The primary and secondary efficacy analysis will be performed on all Subjects in FAS Population (Efficacy Evaluable Population) and PP Population comparing Group 1 (Galnobax® plus SoC) and Group 2 (SoC only). All the statistical analysis will be performed using SAS® version 9.4 or later.

The Safety analysis will be performed on all Subjects in ITT Population (Safety Evaluable Population).

9.4.2 ANALYSIS OF THE PRIMARY EFFICACY ENDPOINT

The primary efficacy analysis will be performed on all Subjects in FAS Population (Efficacy Evaluable Population) and PP Population comparing Group 1 (Galnobax® plus SoC) and Group 2 (SoC only) only.

Proportion of Subjects achieving Target Ulcer closure within 12 week Treatment Phase (EOT) = [Number of Subjects having Target Ulcer closed by treatment at or before week 12 (84 ± 3 days)]/[Total Number of Subjects in the Population].

The logistic regression analysis will be used for the primary efficacy analysis for the proportion of Subjects achieving Target Ulcer closure within 12-week Treatment Phase, considering Target Ulcer closed (Yes/No) as dependent variable and treatment group, ulcer type (plantar or non-plantar), and site as independent factors and baseline ulcer size as continuous covariate.

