4 STUDY DESIGN

4.1 OVERALL DESIGN

This Study is a Phase 3, multicenter, randomized, double-blind, parallel-group Study designed to evaluate the safety and efficacy of Galnobax® plus SoC versus only SoC, in treating DFU in adults with diabetes mellitus (DM). In addition, Study is designed to evaluate safety of Vehicle plus SoC versus only SoC in Subjects with DFU to investigate deleterious effects of Vehicle on wound healing, if any.

For this purpose, the Subjects will be randomized in 3:3:1 ratio into one of the following groups:

- Group 1: Galnobax® 14% gel plus SoC
- Group 2: SoC only
- Group 3: Vehicle plus SoC

Total number of Subjects in the Study: This Study will have FAS Population (Efficacy Evaluable Population) of a minimum of 240 Subjects in Group 1 and Group 2 (minimum of 120 in each Group). To ensure this and assuming 20% drop out rate, the population of two groups would be maximum of 300 Subjects. In addition, for investigating the effect of vehicle on wound healing, Vehicle plus SoC group will recruit up to 50 Subjects. Thus, overall 350 Subjects will be recruited in the Study.

No. of investigational sites: This Study will be conducted at approximately 40 sites across India with competitive recruitment amongst sites.

Maximum duration of a Subject in the Study: The maximum total duration of Subject in the Study will be 25 weeks spread over three phases in following sequence:

- Screening Phase of 1-week (7 + 3 days)
- Treatment Phase of a maximum of 12-weeks (84±3 days) starting with Baseline visit
- Follow-Up Phase of 12-weeks (84±5 days). This will comprise of Closure Confirmation period of 4 weeks (28±3 days) and Observation period of 8 weeks (56±5 days).

Subject Number Assignment: The Subjects will be assigned randomization number using an interactive web-based randomization system (IWRs). Prior to randomization, Subjects will be stratified by location (plantar or non-plantar) and size ($<5\text{ cm}^2$ or $\geq 5\text{ cm}^2$) of the Target Ulcer solely for the purpose of bringing homogeneity among the three treatment Groups in proportionately. Once a randomization number has been assigned, it cannot be re-assigned to any other Subject.

Application of Treatment: Subjects in the Study will receive treatment twice daily during the 12-weeks of Treatment Phase or up to the Target Ulcer Closure, whichever is earlier. During this period, the twice daily treatment to the Subjects in all the arms of the Study will be administered

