9.2 SAMPLE SIZE DETERMINATION

This Study will have FAS Population (Efficacy Evaluable Population) of minimum of 240 Subjects (minimum of 120 each in Group 1 and Group 2). To ensure this and assuming 20% drop out rate, the population of two groups would be up to 300 Subjects. For safety analysis of Vehicle of Galnobax®, maximum of 50 Subjects will be recruited in Vehicle plus SoC group. Thus, overall population of maximum of 350 Subjects will be recruited in the Study.

Sample Size Determination and Rationale:

The sample size calculation has two components. One is based on statistical power and the other is based on clinical judgment.

The sample size calculation is based on the primary endpoint for the Study that is proportion of Subjects achieving complete closure of Target Ulcer within 12-week Treatment Phase, as determined by blinded Investigator's assessment.

The sample size is obtained based on the assumption that there will be a clinically meaningful difference of 21%, (i.e., 39% of SoC vs 60% of Galnobax®-treated achieved complete closure of Target Ulcer, odds ratio of 0.65). This assumption is based on the following:

- a. Literature reports from various DFU trials showed that average percent wounds closed using SoC treatment is 24% globally.^{5 27} However, percent wounds closed using SoC treatment in recently completed DFU trial in India is reported to be 37.8%.²⁸ In view of this, it is assumed that 39% wounds may close in the SoC group.
- b. In Phase 1/2 study of Galnobax®, 60% wounds closed within 12-week of Galnobax® treatment. Furthermore, 67% wounds were closed in Galnobax® arm for wounds with wound age > 6 weeks. In view of this, the inclusion criterion is revised to include Subjects with wounds of at least 6 weeks (which was 4 weeks in Phase 1/2 study) and it is assumed that 60% wounds may close in the Galnobax® treatment group.

To meet the Type I error rate of 0.05 (95% confidence interval), 2-sided analysis and 90% power, 120 Efficacy Evaluable Subjects in Group 1 and Group 2 will be required for making the FAS Population in the Study as 240. To accommodate the potential drop outs rate of 20%, a total of 300 Subjects will be randomized in these Groups to ensure more than 90% power for the primary endpoint analysis (i.e., proportion of Subjects achieving Target Ulcer Closure within 12-week Treatment Phase).

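### The trial is sized on a 21-point difference in closure, but the primary analysis plans no adjusted difference with a confidence interval, and its site-term odds ratio is inflated

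*Combined protocol and SAP*

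**What the plan says.** Section 9.2 sets the target as a "clinically meaningful difference of 21%, (i.e., 39% of SoC vs 60% of Galnobax®-treated achieved complete closure of Target Ulcer", and in the same sentence restates it as an "odds ratio of 0.65". The error rates are given as "To meet the Type I error rate of 0.05 (95% confidence interval), 2-sided analysis and 90% power". The outcome of the calculation is that "120 Efficacy Evaluable Subjects in Group 1 and Group 2 will be required for making the FAS Population in the Study as 240", and then: "To accommodate the potential drop outs rate of 20%, a total of 300 Subjects will be randomized in these Groups".

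Section 9.4.2 defines the closure proportion as number closed over number in the population. It then says: "The logistic regression analysis will be used for the primary efficacy analysis for the proportion of Subjects" with closure, on treatment group, ulcer type (plantar or not) and site as factors and baseline ulcer size as a continuous covariate. It names no effect measure, no confidence interval and no conversion to a difference. Section 4.1 puts the number of sites at about 40.

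Section 9.4.1 says categorical data will be shown by treatment group as counts and percentages, and that a separate SAP will give the detailed methods. That SAP is not part of the combined document. The primary objective in Section 3 is framed as a proportion and does not say how the two proportions are to be compared.

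**The concern.** The target is on the scale of percentage points, while the only inferential analysis of the primary endpoint works on the log-odds scale. With closure rates of 39% to 60% the two scales read very differently: the same effect is 21 points, a risk ratio of 1.54 or an odds ratio of 2.35.

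Two features widen the gap. An odds ratio that conditions on prognostic factors is further from 1 than the marginal one even when it is estimated perfectly. And maximum likelihood with about 40 site terms in 240 subjects pushes the estimate further out again. The headline estimate could then look larger than the effect the trial was designed to find, with no planned interval on the scale that clinicians and the sample size use. The odds ratio quoted in Section 9.2, which might serve as a yardstick for the model output, is not the odds ratio of 39% against 60%.

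**Working it through.** **Inputs.** From Section 9.2: 39% and 60%, two-sided 0.05, 90% power, 120 evaluable per arm, 20% dropout. From Section 4.1: "the Subjects will be randomized in 3:3:1 ratio", so the efficacy comparison is 1:1, and about 40 sites.

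**1. The plan's own sample size.** Mean proportion 0.495; sum of variances 0.39×0.61 + 0.60×0.40 = 0.4779.

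n = [1.960×√(2×0.495×0.505) + 1.282×√0.4779]² / 0.21² = (1.386 + 0.886)² / 0.0441, or 118 per arm rounded up. The plan states 120, which gives 90.7% power. A calculation on the log odds ratio gives 121. Dropout: 240/0.80 = 300, as stated. The sample size reproduces.

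**2. The effect on three scales.**
- Difference: 0.60 − 0.39 = 21 points.
- Risk ratio: 0.60/0.39 = 1.54; inverted, 0.39/0.60 = 0.65.
- Odds ratio: (0.60/0.40)/(0.39/0.61) = 2.35; inverted, 0.43.

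The stated 0.65 is therefore the ratio of proportions. Read literally as an odds ratio, starting from 39%: odds 0.6393/0.65 = 0.9836, or 49.6% closure. That is a difference of 10.6 points, which would need 461 per arm; 120 per arm would have 38% power.

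**3. The interval that is missing.** If 60% and 39% are observed with 120 per arm, SE = √(0.4779/120) = 0.063. The unadjusted 95% CI is 21 ± 12.4 points, or about 8.6 to 33.4.

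**4. Conditional against marginal odds ratio.** For a marginal 39% against 60%, the conditional odds ratio is 2.35, 2.47, 2.80 or 3.33 when the prognostic score has an assumed SD of 0, 0.5, 1.0 or 1.5 on the logit.

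**5. The planned model with site terms.** 240/40 = 6 subjects per site, about 3 per arm. Simulated trials used 240 subjects, 40 sites and a marginal truth of 39% against 60%. The assumptions were a size effect of 0.5 per SD and a site SD of 0, 0.5 or 1.0 on the logit. With sites of equal expected size, 400 trials per row:

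| Site SD | True conditional OR | Median fitted OR | Mean standardised difference |
|---|---|---|---|
| 0 | 2.47 | 3.10 | 21.2 points |
| 0.5 | 2.58 | 3.30 | 21.4 points |
| 1.0 | 2.91 | 3.72 | 20.8 points |

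In at least 99% of these trials some site had all or none of its ulcers closed. With sites of unequal size the median fitted odds ratio was 2.9 to 3.5 over the same range of site SD, and the standardised difference was 20.0 to 20.5 points against a true 21. Without site terms the median odds ratio was 2.4 to 2.5.

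**6. Does standardising the planned model suffice?** Not for the interval. With site terms, the model-based 95% CI for the standardised difference covered the truth in 90 to 94% of trials and excluded zero in 6.5 to 8.0% under no effect. Without site terms these were about 95% and 5%.

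**The case against.** The best reply is that the difference can already be read. Section 9.4.2 defines the proportion closed and Section 9.4.1 promises percentages by group, so subtraction gives a crude difference and two counts give an interval. This stands. A reader might infer that the result cannot be set against the target at all, and the documents do not support that. What is missing is a pre-specified adjusted difference and any planned interval for it.

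A reader might also infer that success is defined as reaching 21 points. It is not: the 21 points is a design assumption in Section 9.2, and Sections 3 and 9.1 set no margin.

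The effect measure may yet appear in the separate SAP. That is possible and lowers confidence somewhat, but Section 9.4.2 is the text that the SAP will elaborate, and it already fixes the site terms.

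Finally, the size of the inflation depends on assumed site and covariate effects, and part of it comes from how site is handled and not from the choice of scale. Both remarks are fair. The direction did not change over the range tried, and even with no true site variation the fitted odds ratio was too large.

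**Conclusion.** The gap is real and should be closed before database lock. The only inferential analysis planned for the primary endpoint yields a conditional odds ratio that, with about six subjects per site, is biased away from 1: a simulated median of 2.9 to 3.5 against true conditional values of 2.5 to 2.9 and a marginal 2.35. No adjusted difference and no interval is specified on the 21-point scale, and the one odds-scale benchmark is mislabelled (0.65 where the odds ratio is 0.43).

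The simulated figures rest on assumed site SDs of 0 to 1.0 and an assumed size effect; the arithmetic on 39%, 60% and 0.65 needs no assumption. A reader might infer from the wrong odds ratio that the trial is underpowered. It is not, on its own assumptions: 120 per arm matches 39% against 60%, and does not come from an odds ratio of 0.65.

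**What to change.** In Section 9.4.2, name the covariate-standardised difference in closure proportions (Galnobax plus SoC minus SoC) with its 95% CI as the effect estimate for the primary endpoint, with the odds ratio as supportive. Obtain it from the logistic model with treatment, ulcer type and baseline ulcer size, without about 40 separate site terms, or with small sites pooled by a rule fixed in advance. State how the interval is computed. Site is not a stratification factor in Section 9.2.1, so leaving out its separate terms drops none of the factors used in randomisation. Also state which model carries the primary test, so that the p-value and the interval do not come from different models.

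In Section 9.2, change the odds ratio of 0.65 to a risk ratio of 0.65 (odds ratio 0.43, or 2.35 for Galnobax over SoC).

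The cost is wording and a few lines of code. No data are added and the sample size is unchanged (118 per arm recomputed, 120 planned). The headline figure will look smaller than an odds ratio would.
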